**P15-743 (HCV RWE) \_ STATISTICAL ANALYSIS PLAN \_ final 2.0 \_ 02 Feb 2018**

Similar to table 3.10. 1.1, the following tables will be constructed:

for the question “Taking an active role in my own health care is the most important thing that affects my health”  
Table 3.12.2 PAM 13. Question 2

for the question “I am confident I can help prevent or reduce problems associated with my health”  
Table 3.12.3 PAM 13. Question 3

for the question “I know what each of my prescribed medications do”  
Table 3.12.4 PAM 13. Question 4

for the question “I am confident that I can tell whether I need to go to the doctor or whether I can take care of health problem myself”  
Table 3.12.5 PAM 13. Question 5

for the question “I am confident that I can tell a doctor concerns I have even when he or she does not ask”  
Table 3.12.6 PAM 13. Question 6

for the question “I am confident that I can follow through on medical treatments I may need to do at home”  
Table 3.12.7 PAM 13. Question 7

for the question “I understand my health problems and what causes them”  
Table 3.12.8 PAM 13. Question 8

for the question “I know what treatments are available for my health problems”  
Table 3.12.9 PAM 13. Question 9

for the question “I have been able to maintain (keep up with) lifestyle changes, like eating right or exercising”  
Table 3.12.10 PAM 13. Question 10

for the question “I know how to prevent problems with my health”  
Table 3.12.11 PAM 13. Question 11

for the question “I am confident I can figure out solutions when new problems arise with my health”  
Table 3.12.12 PAM 13. Question 12

for the question “I am confident that I can maintain lifestyle changes, like eating and exercising, even during times of stress”  
Table 3.12.13 PAM 13. Question 13

**P15-743 (HCV RWE) \_ STATISTICAL ANALYSIS PLAN \_ final 2.0 \_ 02 Feb 2018**

AbbVie Ltd  
P15-743  
**Table 3.12.14PAM 13. Score**  
The core population  
Page X of X

| Visit Parameter | ABBVIE REGIMEN + RBV
12 weeks
(N = XX) | ABBVIE REGIMEN - RBV
12 weeks
(N = XX) | Overall
(N = XX) |
|-----------------|--|--|---------------------|
| Baseline |  |  |                     |
| n               | XX   | XX   | XX                  |
| Mean            | XX.X   | XX.X   | XX.X                |
| SD              | XX.XX  | XX.XX  | XX.XX               |
| Median          | XX.X   | XX.X   | XX.X                |
| IQR             | XX.X   | XX.X   | XX.X                |
| Min             | XX   | XX   | XX                  |
| Max             | XX   | XX   | XX                  |
| EoT      |  |  |                     |
| n               | XX   | XX   | XX                  |
| Mean            | XX.X   | XX.X   | XX.X                |
| SD              | XX.XX  | XX.XX  | XX.XX               |
| Median          | XX.X   | XX.X   | XX.X                |
| IQR             | XX.X   | XX.X   | XX.X                |
| Min             | XX   | XX   | XX                  |
| Max             | XX   | XX   | XX                  |

N: the number of subjects in the core population.  
n: the number of valid measurements.  
EoT: end of treatment.

Program code, date, time

Data extracted: DD.MM.YYYY

**P15-743 (HCV RWE) \_ STATISTICAL ANALYSIS PLAN \_ final 2.0 \_ 02 Feb 2018**

AbbVie Ltd  
P15-743  
**Table 3.12.15PAM 13. Score. ANCOVA results**  
The core population  
Page X of X

| Time point | Regimen group / Parameter                     | n  | LS mean | 95% CI          | Difference between Regimen groups | p-value         |
|------------|---|----|---------|-----------------|-----------------------------------|-----------------|
| EoT        | Regimen group 1                               | XX | XX.XX   | (XX.XX - XX.XX) | XX.XX                             | (XX.XX - XX.XX) |
|            | Regimen group 2                               | XX | XX.XX   | (XX.XX - XX.XX) |                                   |                 |
|            | ...   |    |         |                 |                                   |                 |
|            | Covariate (baseline value)                    |    |         |                 |                                   | X.XXXX          |
|            | Fixed factor 1                                |    |         |                 |                                   | X.XXXX          |
|            | ...   |    |         |                 |                                   | X.XXXX          |
|            | Comparison: Regimen group 1 - Regimen group 2 |    |         |                 |                                   | X.XXXX          |
|            | ...   |    |         |                 |                                   |                 |

n: the number of valid measurements.  
95% CI: 95% confidence interval.  
EoT: end of treatment.  
LS mean: list square mean - mean value adjusted for the effect of the covariate.

Program code, date, time Data extracted: DD.MM.YYYY

**P15-743 (HCV RWE) \_ STATISTICAL ANALYSIS PLAN \_ final 2.0 \_ 02 Feb 2018**

AbbVie Ltd  
P15-743  
**Table 3.12.16PAM 13. Level of activation**  
The core population  
Page X of X

| Visit
Parameter | ABBVIE REGIMEN + RBV          |  | ABBVIE REGIMEN - RBV          |  | Overall
(N = XX)
n (%) |
|--------------------|-------------------------------|--|-------------------------------|--|------------------------------|
|                    | 12 weeks
(N = XX)
n (%) |  | 12 weeks
(N = XX)
n (%) |  |                              |
| Baseline           |                               |  |                               |  |                              |
| n                  | XX                            |  | XX                            |  | XX                           |
| Level 1            | XX (XX.X)                     |  | XX (XX.X)                     |  | XX (XX.X)                    |
| Level 2            | XX (XX.X)                     |  | XX (XX.X)                     |  | XX (XX.X)                    |
| Level 3            | XX (XX.X)                     |  | XX (XX.X)                     |  | XX (XX.X)                    |
| Level 4            | XX (XX.X)                     |  | XX (XX.X)                     |  | XX (XX.X)                    |
| EoT                |                               |  |                               |  |                              |
| n                  | XX                            |  | XX                            |  | XX                           |
| Level 1            | XX (XX.X)                     |  | XX (XX.X)                     |  | XX (XX.X)                    |
| Level 2            | XX (XX.X)                     |  | XX (XX.X)                     |  | XX (XX.X)                    |
| Level 3            | XX (XX.X)                     |  | XX (XX.X)                     |  | XX (XX.X)                    |
| Level 4            | XX (XX.X)                     |  | XX (XX.X)                     |  | XX (XX.X)                    |

N: the number of subjects in the core population.  
n: the number of valid measurements.  
EoT: end of treatment.  
Percentages are calculated from the number of subjects in the core population.

Program code, date, time

Data extracted: DD.MM.YYYY

**P15-743 (HCV RWE) \_ STATISTICAL ANALYSIS PLAN \_ final 2.0 \_ 02 Feb 2018**

**The target population**

Similar to table 3.12.\*.\*, the following tables will be constructed:

- Table 3.13.1 PAM 13. Question 1
- Table 3.13.2 PAM 13. Question 2
- Table 3.13.3 PAM 13. Question 3
- Table 3.13.4 PAM 13. Question 4
- Table 3.13.5 PAM 13. Question 5
- Table 3.13.6 PAM 13. Question 6
- Table 3.13.7 PAM 13. Question 7
- Table 3.13.8 PAM 13. Question 8
- Table 3.13.9 PAM 13. Question 9
- Table 3.13.10 PAM 13. Question 10
- Table 3.13.11 PAM 13. Question 11
- Table 3.13.12 PAM 13. Question 12
- Table 3.13.13 PAM 13. Question 13

Table 3.13.14PAM 13. Score

Table 3.13.15 PAM 13. Score. ANCOVA results

Table 3.13.16PAM 13. Level of activation

**P15-743 (HCV RWE)\_ STATISTICAL ANALYSIS PLAN \_ final 2.0 \_ 02 Feb 2018**

**The core population with sufficient follow-up data**

Similar to table 3.12.\*.\*, the following tables will be constructed:

- Table 3.14.1 PAM 13. Question 1
- Table 3.14.2 PAM 13. Question 2
- Table 3.14.3 PAM 13. Question 3
- Table 3.14.4 PAM 13. Question 4
- Table 3.14.5 PAM 13. Question 5
- Table 3.14.6 PAM 13. Question 6
- Table 3.14.7 PAM 13. Question 7
- Table 3.14.8 PAM 13. Question 8
- Table 3.14.9 PAM 13. Question 9
- Table 3.14.10 PAM 13. Question 10
- Table 3.14.11 PAM 13. Question 11
- Table 3.14.12 PAM 13. Question 12
- Table 3.14.13 PAM 13. Question 13

Table 3.14.14PAM 13. Score

Table 3.14.15PAM 13. Score. ANCOVA results

Table 3.14.16PAM 13. Level of activation

 If the target population and the core population with sufficient follow-up data will be equal then the tables for the target population will be presented only and it will be noted in the footnotes in presented tables.

P15-743 (HCV RWE) \_ STATISTICAL ANALYSIS PLAN \_ final 2.0 \_ 02 Feb 2018

Exposure

AbbVie LLC  
P15-743 (HCV RWE)  
**Table 4.1 AbbVie REGIMEN and Ribavirin intake**  
The safety population  
Page X of X

|   | ABBVIE REGIMEN + RBV
12 weeks
(N = XX) | ABBVIE REGIMEN - RBV
12 weeks
(N = XX) | Overall
(N = XX) |
|---|--|--|---------------------|
| Actual duration ABBVIE REGIMEN [1]                        | ...  | ...  | ...                 |
| n   | XX   | XX   | XX                  |
| Mean  | XX.X   | XX.X   | XX.X                |
| SD  | XX.XX  | XX.XX  | XX.XX               |
| Median  | XX.X   | XX.X   | XX.X                |
| IQR   | XX.X   | XX.X   | XX.X                |
| Min   | XX   | XX   | XX                  |
| Max   | XX   | XX   | XX                  |
| Subjects with collected deviating duration reasons        | XX (XX.X)                                    | XX (XX.X)                                    | XX (XX.X)           |
| Reasons for deviating duration:                           |  |  |                     |
| AE or SAE (Physician decision)                            | XX (XX.X)                                    | XX (XX.X)                                    | XX (XX.X)           |
| Virological non-response (Physician decision)             | XX (XX.X)                                    | XX (XX.X)                                    | XX (XX.X)           |
| Rebound or breakthrough (Physician decision)              | XX (XX.X)                                    | XX (XX.X)                                    | XX (XX.X)           |
| Resistance to DAA (Physician decision)                    | XX (XX.X)                                    | XX (XX.X)                                    | XX (XX.X)           |
| Patient refused to continue treatment                     | XX (XX.X)                                    | XX (XX.X)                                    | XX (XX.X)           |
| Patient withdrew consent to participate in the study      | XX (XX.X)                                    | XX (XX.X)                                    | XX (XX.X)           |
| Lost to follow-up   | XX (XX.X)                                    | XX (XX.X)                                    | XX (XX.X)           |
| ...   | ...  | ...  | ...                 |
| PARITAPREVIR/R-OMBITASVIR                                 |  |  |                     |
| Subjects with intake missing for at least 7 days in a row | XX (XX.X)                                    | XX (XX.X)                                    | XX (XX.X)           |
| Percentage of target dose taken (%)                       |  |  |                     |
| Weeks 1-4   |  |  |                     |
| n   | XX   | XX   | XX                  |
| Mean  | XX.X   | XX.X   | XX.X                |
| SD  | XX.XX  | XX.XX  | XX.XX               |
| Median  | XX.X   | XX.X   | XX.X                |
| IQR   | XX.X   | XX.X   | XX.X                |
| Min   | XX   | XX   | XX                  |
| Max   | XX   | XX   | XX                  |
| Weeks 5-8   |  |  |                     |
| ...   |  |  |                     |

**P15-743 (HCV RWE) \_ STATISTICAL ANALYSIS PLAN \_ final 2.0 \_ 02 Feb 2018**

|   | ABBVIE REGIMEN + RBV
12 weeks
(N = XX) | ABBVIE REGIMEN - RBV
12 weeks
(N = XX) | Overall
(N = XX) |
|---|--|--|---------------------|
| Weeks 9-12  |  |  | ...                 |
| ...   | XX   | XX   | XX                  |
| ...   | XX.X   | XX.X   | XX.X                |
| DASABUVIR   |  |  |                     |
| Subjects with intake missing for at least 7 days in a row | XX (XX.X)                                    | XX (XX.X)                                    | XX (XX.X)           |
| Percentage of target dose taken (%)                       |  |  |                     |
| Weeks 1-4   | XX   | XX   | XX                  |
| ...   |  |  |                     |
| Weeks 5-8   | XX   | XX   | XX                  |
| ...   | XX.X   | XX.X   | XX.X                |
| Weeks 9-12  | XX.XX  | XX.XX  | XX.XX               |
| ...   | XX.X   | XX.X   | XX.X                |
| ...   |  |  |                     |
| RIBAVIRIN   |  |  |                     |
| Percentage of target dose taken (%)                       |  |  |                     |
| Weeks 1-4   | XX   | XX   | XX                  |
| ...   |  |  |                     |
| Weeks 5-8   | XX   | XX   | XX                  |
| ...   | XX.X   | XX.X   | XX.X                |
| Weeks 9-12  | XX.XX  | XX.XX  | XX.XX               |
| ...   | XX.X   | XX.X   | XX.X                |
| ...   |  |  |                     |

N: the number of subjects in the target population.  
n: the number of subjects within a specific category. Percentages were calculated as (100 x n/N).  
[1] This parameter is calculated as interval (in days) between date of first intake and date of last intake of treatment.

**P15-743 (HCV RWE) \_ STATISTICAL ANALYSIS PLAN \_ final 2.0 \_ 02 Feb 2018**

**Adverse events**

AbbVie LLC  
P15-743 (HCV RWE)  
**Table 4.2.1 Adverse events**  
The safety population  
Page X of X

| System organ class (SOC)
Preferred term (PT) | ABBVIE REGIMEN + RBV           |              | ABBVIE REGIMEN - RBV           |              | Overall
(N=XX)
n (%) /E |
|---|--------------------------------|--------------|--------------------------------|--------------|-------------------------------|
|   | 12 weeks
(N=XX)
n (%) /E | XX(XX.X) /XX | 12 weeks
(N=XX)
n (%) /E | XX(XX.X) /XX |                               |
| Total [1]                                       | XX(XX.X) /XX                   | XX(XX.X) /XX | XX(XX.X) /XX                   | XX(XX.X) /XX | XX(XX.X) /XX                  |
| System organ class 1                            | XX(XX.X) /XX                   | XX(XX.X) /XX | XX(XX.X) /XX                   | XX(XX.X) /XX | XX(XX.X) /XX                  |
| Preferred term A                                | XX(XX.X) /XX                   | XX(XX.X) /XX | XX(XX.X) /XX                   | XX(XX.X) /XX | XX(XX.X) /XX                  |
| Preferred term B                                | ...                            | ...          | ...                            | ...          | ...                           |
| ...   | ...                            | ...          | ...                            | ...          | ...                           |
| System organ class 2                            | ...                            | ...          | ...                            | ...          | ...                           |
| ...   | ...                            | ...          | ...                            | ...          | ...                           |
| ...   | ...                            | ...          | ...                            | ...          | ...                           |

N: the number of patients in the safety population.  
n: the number of patients who have AE with appropriate SOC/PT. Percentages are calculated as (100 x n/N) .  
E: the number of AE episodes, which have an appropriate SOC and/or PT.  
Patients with several AEs having the same SOC and PT are accounted only once for appropriate SOC and PT.  
[1] The Total line displays the number (n) and the proportion (%) of patients who have at least on AE as well as the total number of AE episodes in the study.  
The coding is carried out by the dictionary MedDRA v.20.1.  
The table does not include AEs that occurred prior to the first intake of the study drug.  
The data is sorted alphabetically: first by SOC, then by PT.

Program code, date, time  
Data extracted: DD.MM.YYYY

Similar to table 4.2.1, table 4.2.2 will be constructed:

**Table 4.2.2 Serious adverse events**

**P15-743 (HCV RWE) \_ STATISTICAL ANALYSIS PLAN \_ final 2.0 \_ 02 Feb 2018**

AbbVie LLC

P15-743 (HCV RWE)

**Table 4.3.1 Adverse events by relationship to ABBVIE REGIMEN**

The safety population

Page X of X

| System Organ Class (SOC)
Preferred term (PT) | Relationship
to the study drug | ABBVIE REGIMEN + RBV           |                                | ABBVIE REGIMEN - RBV           |                                | Overall
(N=XX)
n (%) /E |
|---|-----------------------------------|--------------------------------|--------------------------------|--------------------------------|--------------------------------|-------------------------------|
|   |                                   | 12 weeks
(N=XX)
n (%) /E | 12 weeks
(N=XX)
n (%) /E | 12 weeks
(N=XX)
n (%) /E | 12 weeks
(N=XX)
n (%) /E |                               |
| Total [1]                                       | Reasonable possibility            | XX (XX.X) /XX                  | XX (XX.X) /XX                  | XX (XX.X) /XX                  | XX (XX.X) /XX                  | XX (XX.X) /XX                 |
|   | No reasonable possibility         | XX (XX.X) /XX                  | XX (XX.X) /XX                  | XX (XX.X) /XX                  | XX (XX.X) /XX                  | XX (XX.X) /XX                 |
|   | Total                             | XX (XX.X) /XX                  | XX (XX.X) /XX                  | XX (XX.X) /XX                  | XX (XX.X) /XX                  | XX (XX.X) /XX                 |
| System Organ Class 1                            | Reasonable possibility            | XX (XX.X) /XX                  | XX (XX.X) /XX                  | XX (XX.X) /XX                  | XX (XX.X) /XX                  | XX (XX.X) /XX                 |
|   | No reasonable possibility         | XX (XX.X) /XX                  | XX (XX.X) /XX                  | XX (XX.X) /XX                  | XX (XX.X) /XX                  | XX (XX.X) /XX                 |
|   | Total                             | XX (XX.X) /XX                  | XX (XX.X) /XX                  | XX (XX.X) /XX                  | XX (XX.X) /XX                  | XX (XX.X) /XX                 |
| Preferred term A                                | Reasonable possibility            | XX (XX.X) /XX                  | XX (XX.X) /XX                  | XX (XX.X) /XX                  | XX (XX.X) /XX                  | XX (XX.X) /XX                 |
|   | No reasonable possibility         | XX (XX.X) /XX                  | XX (XX.X) /XX                  | XX (XX.X) /XX                  | XX (XX.X) /XX                  | XX (XX.X) /XX                 |
|   | Total                             | XX (XX.X) /XX                  | XX (XX.X) /XX                  | XX (XX.X) /XX                  | XX (XX.X) /XX                  | XX (XX.X) /XX                 |
| Preferred term B                                | Reasonable possibility            | XX (XX.X) /XX                  | XX (XX.X) /XX                  | XX (XX.X) /XX                  | XX (XX.X) /XX                  | XX (XX.X) /XX                 |
|   | ...                               | ...                            | ...                            | ...                            | ...                            | ...                           |
|   | Reasonable possibility            | XX (XX.X) /XX                  | XX (XX.X) /XX                  | XX (XX.X) /XX                  | XX (XX.X) /XX                  | XX (XX.X) /XX                 |
| System Organ Class 2                            | Reasonable possibility            | XX (XX.X) /XX                  | XX (XX.X) /XX                  | XX (XX.X) /XX                  | XX (XX.X) /XX                  | XX (XX.X) /XX                 |
|   | ...                               | ...                            | ...                            | ...                            | ...                            | ...                           |
|   | Reasonable possibility            | XX (XX.X) /XX                  | XX (XX.X) /XX                  | XX (XX.X) /XX                  | XX (XX.X) /XX                  | XX (XX.X) /XX                 |

N: the number of patients in the safety population.

n: the number of patients who have AE with appropriate SOC/PT. Percentages are calculated as (100 x n/N).

E: the number of AE episodes, which have an appropriate SOC and/or PT.

Each SOC/PT category includes only AEs with the highest relationship to the study drug in each patient. Each patient is counted only once in the Total lines and in the lines for each SOC or SOC/PT categories. Thus, if patient has several AEs with the same SOC and PT but different relationship to the drug, only the AEs with maximum relationship will be accounted, while each patient will be accounted only once in line which corresponds the highest relationship of his AEs.

[1] The Total lines displays the number (n) and the proportion (%) of patients who have AEs. Each patient is counted once in line which corresponds the highest relationship of all his AEs. #E displays the number of all AEs episodes with appropriate relationship to the drug in the study. The coding is carried out by the dictionary MedDRA v.20.1.

The table does not include AEs that occurred prior to the first intake of the study drug.

**P15-743 (HCV RWE) \_ STATISTICAL ANALYSIS PLAN \_ final 2.0 \_ 02 Feb 2018**

---

The data is sorted alphabetically: first by SOC, then by PT and relationship to the drug.

Program code, date, time

Data extracted: DD.MM.YYYY

Similar to table 4.3.1, the following tables will be constructed:

Table 4.3.2 Serious adverse events by relationship to ABBVIE REGIMEN

Table 4.3.3 Adverse events by relationship to Ribavirin

Table 4.3.4 Serious adverse events by relationship to Ribavirin

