## 6 Analysis populations

*The target population (TP)* – all patients, who fulfill the following criteria:

- treatment-naïve or treatment-experienced adult (age at least 18 years) male or female patients with confirmed CHC with genotype 1 (1a and/or 1b) only, receiving combination therapy with the interferon-free ABBVIE REGIMEN  $\pm$  RBV according to standard of care and in line with the current local label. The prescribed ABBVIE REGIMEN needs to be known;
- if RBV is co-administered with the ABBVIE REGIMEN, it has been prescribed in line with the current local label (with special attention to contraception requirements and contraindication during pregnancy);
- patients with voluntarily signed and dated a patient authorization to use and/or disclosure his/her anonymized health data (or informed consent) prior to inclusion into the study;
- patients must not be participating or intending to participate in a concurrent interventional therapeutic study.

Patients who prematurely discontinue earlier than  $\leq$ study day 55 (for 12 weeks treatment) or  $\leq$ study day 139 (for 24 weeks treatment) will be used in analyses on the population with actual EoT time point without windowing conventions adjustment for EoT.

*The core population (CP)* – all patients of the TP, who have started the treatment combination recommended in the current local label for their disease characteristics. Patients, who fulfill at least one of the following conditions, will be excluded from the CP:

- patients with unknown fibrosis status;
- cirrhotic patients with genotype 1a not receiving ribavirin;
- patients with genotype 1 for whom two direct-acting antiviral agents regimen (2DAA) instead of 3DAA is prescribed;
- patients with EoT  $\leq$ study day 55 (for 12 weeks treatment) or  $\leq$ study day 139 (for 24 weeks treatment).

*The safety population (SP)* – all patients who received at least one dose of the ABBVIE REGIMEN.

 This table is based on the table 4 “Analysis time windows” of clinical study Protocol.

 These time windows are intended for the CP allocation filter only. In case of the TP, all patients will be used for the analysis regardless of actual EoT day relevance to EoT time windows.

 This section is based on the sections 9.7.1 “Analysis population, time windows and handling of missing data” and 9.2.1 “Target population” of clinical study Protocol.

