## 11 Safety analysis

Safety analysis will be conducted on *the safety population (SP)*. The results will be reported overall and for scheduled treatment combination ( $\pm$  RBV) and duration (12 or 24 weeks) groups.

The following parameters will be analyzed:

- study drug exposure;
- adverse events;
- pregnancies;
- clinical laboratory evaluations.

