### 11.2 Adverse Events

Only treatment-emergent adverse events will be analyzed.

*Treatment-emergent AE* is any reported event that begins or worsens in severity after initiation of study drug through 30 days post-study drug dosing.

All analyzed AEs will be coded using the MedDRA version 20.0 (or further updating) and tabulated in the report with grouping by primary system organ class (SOC) and preferred term (PT).

The frequency of a specific AE occurrence will be presented by the proportion of patients with this AE emergence as well as the total number of episodes this AE for a diagnosis.

The following tables with descriptive statistics in accordance with section 7.1 will be presented:

- all AE / SAE;
- AE / SAE by severity;
- AE / SAE by relationship to the study drug.

Tables of AE/SAE by severity (relationship to the study drug) will be prepared using the following rules. Each SOC / PT category will include only the AEs with the highest severity (relationship to the drug) in each patient, while in the Total category all AEs of this patient will be considered. At the same time, each patient will be counted only once with highest severity (relationship to the study drug) in each SOC and each PT level as well as Total level.

Also all AEs will be presented in listings. Additional listings for unintended medication errors will be provided.

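### The Overall column of the two ribavirin-relationship tables is diluted by patients without ribavirin, and the SOC/PT rows of the relationship and severity tables omit episodes that E is defined to count

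*SAP*

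**What the plan says.** **Ribavirin tables.** After Table 4.3.1 (adverse events by relationship to the ABBVIE REGIMEN), SAP section 18 states "Similar to table 4.3.1, the following tables will be constructed" and lists, among others, "Table 4.3.3 Adverse events by relationship to Ribavirin" and Table 4.3.4, its serious-event counterpart. The Table 4.3.1 footnote sets "N: the number of patients in the safety population", with percentages as 100 times n over N. SAP section 6 defines that population as "all patients who received at least one dose of the ABBVIE REGIMEN"; a ribavirin dose is not required. On columns, SAP section 11 says "The results will be reported overall and for scheduled treatment combination", with or without RBV, and by duration. The shell accordingly has a +RBV column, a −RBV column and an Overall column.

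**Episode counts.** SAP 11.2 says each adverse event will be shown both as a proportion of patients and as a total number of episodes. For the severity and relationship tables it then says "Each SOC / PT category will include only the AEs with the highest severity (relationship to the drug) in each patient", whereas the Total category takes in all of the patient's events. The footnotes of Tables 4.3.1 and 4.4.1 repeat this rule. The same footnotes, like that of Table 4.2.1, define "E: the number of AE episodes, which have an appropriate SOC and/or PT".

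**Protocol.** Section 9.7.7 counts a patient once per preferred term, at the most severe or most related event, and once per SOC. It asks for numbers and percentages of patients, stratified by type of combination and scheduled duration. It does not ask for episode counts.

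**The concern.** Describing tolerability of the regimen with and without ribavirin is a secondary objective. The protocol's background section attributes many of the adverse events seen in Phase III to ribavirin, so the ribavirin-relationship tables will be read closely.

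First, a percentage in a table titled by relationship to ribavirin is naturally read as a rate among people exposed to ribavirin. With the safety population as denominator, the Overall column is not that rate. It moves with the prescribing mix as well as with tolerability.

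Second, the single label E carries two meanings: all episodes in Tables 4.2.1 and 4.2.2 and in the Total block, but only highest-category episodes in the SOC and PT rows of the 4.3 and 4.4 series. Tables from one report would then show different episode counts for the same term under the same footnote.

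**Working it through.** The shells hold placeholders only, so there is no printed figure to reproduce. The check applies the stated rules.

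**1. Denominator of Tables 4.3.3 and 4.3.4**

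Inputs:
- N for the Overall column is the safety population (Table 4.3.1 footnote and SAP section 6).
- For illustration, N = 158, the planned enrolment (SAP 4.2).
- The share f taking ribavirin is not in the documents. Assumed range: 10% to 90%.
- The proportion of recipients with a ribavirin-related event is not in the documents. Assumed: about 30%.

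Let k be the number of patients with a ribavirin-related event, all of them recipients, and N_R the number of recipients. Then

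Overall % = 100·k/N = (N_R/N) × (100·k/N_R) = f × rate among recipients.

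With counts rounded to whole patients:

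| f | Recipients N_R | k | k/N_R | Overall k/158 |
|---|---|---|---|---|
| 0.10 | 16 | 5 | 31.25% | 3.2% |
| 0.25 | 40 | 12 | 30.0% | 7.6% |
| 0.50 | 79 | 24 | 30.4% | 15.2% |
| 0.75 | 118 | 35 | 29.7% | 22.2% |
| 0.90 | 142 | 43 | 30.3% | 27.2% |

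Relative to the rate among recipients, the Overall figure is too low by a factor of 1/f: tenfold at f = 0.10, twofold at 0.50 and about 1.1-fold at 0.90. That factor does not depend on the assumed 30%. The +RBV column has its own N and gives k/N_R directly, provided patients took ribavirin as scheduled.

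**2. Episode counts in the 4.3 and 4.4 series**

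A simple case: a patient with three mild headaches and one severe. Table 4.2.1 gives E = 4 for headache. The headache rows of Table 4.4.1 give 1 severe, 0 mild and a row total of 1. The Total block of Table 4.4.1 gives 4.

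An invented listing of six episodes in one SOC, with terms A and B:
- Patient 1: A related and severe; A unrelated and mild, twice; B unrelated and mild.
- Patient 2: A unrelated and moderate; A unrelated and mild.

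Applying the highest-category rule within each patient at each level:

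| Count of E | By relationship | By severity |
|---|---|---|
| Total block | 6 (1 related, 5 not) | 6 (1 severe, 1 moderate, 4 mild) |
| SOC row total | 3 (1 related, 2 not) | 2 (1 severe, 1 moderate) |
| Sum of PT row totals | 4 (A: 1 related, 2 not; B: 1 not) | 3 (A: 1 severe, 1 moderate; B: 1 mild) |

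Four things follow:
- The SOC and PT totals fall short of the six episodes that the footnote's definition of E would give.
- The PT rows add to more than their own SOC row (4 against 3, and 3 against 2), because the maximum is taken separately at each level.
- The related count (1) and the severe count (1) are complete. An event in the top category is by definition at the patient's maximum and is never dropped.
- Patient counts are untouched. Each patient still appears once per SOC and once per PT, as protocol 9.7.7 requires.

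**The case against.** The case against is substantial, and much of it stands.

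- **The rate a reader needs is already printed.** The +RBV column sits beside Overall with its own N, and the protocol asks for the stratified result; the Overall column is an SAP addition. This is right, and it confines the first point to one column of two tables.
- **The Overall figure is labelled.** The footnote states N, so the figure is correctly computed as a share of all treated patients. That is true. Even so, a ribavirin-attribution percentage over a mixed group answers no stated objective and invites misreading.
- **Patients in the −RBV column might have received ribavirin.** Columns follow the scheduled combination, and the documents do not say that nobody scheduled without ribavirin ever took it. So it cannot be said that no patient there could have a ribavirin-related event. The dilution depends on who actually took the drug.
- **The episode rule is disclosed, and full counts appear elsewhere.** Table 4.2.1, Table 4.2.2 for serious events and the listings have no such filter. That also stands. It is not a hidden loss, but disclosure does not reconcile the rule with the definition of E in the same footnote.

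A reader might go further and infer that ribavirin-related episodes are undercounted, that adverse event rates in general are too low, or that the SAP breaks the protocol's counting rule. The documents support none of these. Rows for reasonable possibility and severe are complete, the dilution does not reach the ABBVIE REGIMEN or severity tables, and the patient rule is implemented as the protocol sets it. Because the protocol requests no episode counts, the conflict over E lies within the SAP.

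**Conclusion.** Both points hold in limited form.

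1. In Tables 4.3.3 and 4.3.4 the Overall percentage equals the rate among ribavirin recipients times the share who took ribavirin. Its size cannot be fixed from the documents because that share is not given; the figures above rest on an assumed share, an assumed 30% event rate and the planned 158 patients. The +RBV column is sound if treatment followed the schedule.
2. In the 4.3 and 4.4 series, E is too low in the rows for no reasonable possibility, mild and moderate, and in the SOC and PT row totals, whenever a patient also has a higher-category event in the same SOC or PT. Those counts will not agree with Tables 4.2.1 and 4.2.2 or with the Total block, and PT counts can exceed their SOC count. How often this happens depends on repeat events, on which the documents give nothing.

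No primary estimate or test depends on these tables. The plan as written would nevertheless print figures that mislead in one column and contradict their own footnotes in others.

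**What to change.** - **Tables 4.3.3 and 4.3.4:** set N to safety-population patients who received at least one dose of ribavirin, state this in the footnote, and drop the −RBV column or mark it not applicable.
- **SAP 11.2 and the footnotes of the 4.3 and 4.4 series:** keep the worst-event rule for n (%) only. For E, count every episode under its own severity or relationship, so that SOC and PT totals agree with Tables 4.2.1 and 4.2.2 and PT counts add to their SOC.

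The cost is one population filter, one counting line in the adverse event programs and edits to the footnotes. No new data are needed. SAP section 2 permits revision before the database soft lock; a later change would have to be explained in the study report.
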